At the second study call, participants ($N=608$) will be randomized to one level of each of 4 factors (see Table 2): 1) Medication Type (Varenicline vs. C-NRT), 2) Preparation Medication (4 weeks vs. Standard), 3) Medication Duration (Extended vs. Standard), and 4) Counseling (Intensive vs. Minimal). Participants will complete phone assessments one week pre-quit, during the first week post-target quit date (TQD) and at Weeks 2, 4, 12, 20, 26, and 52 post-TQD.

Assessments

Call 1. At Call 1, participants will complete the phone screen, complete the oral consent and HIPAA authorization process, and complete a brief demographics assessment. After this call, participants will be mailed a Study Information Sheet that contains all of the information related to the study. They will also be sent information on how to use WebEx so they can have video visits if they so choose.

Call 2. Participants will answer questions about their smoking and other tobacco use history, their self-efficacy and motivation, their physical and emotional health, the impact of Covid-19 on their life and their beliefs about Covid-19 and smoking, and their satisfaction with their health care and they will complete the Fagerström Test of Cigarette Dependence¹¹⁷ (see Table 1). Participants will be randomized to their treatment condition, set a target quit date, and be educated about their assigned medication (including how and when to request refills).

Calls 3-6. Participants will receive a call one week pre-quit, during the first week post-target quit date (TQD) and at Weeks 2 and 4 from their Health Counselor. This research staff member will assess: a daily smoking calendar using timeline follow-back¹¹⁸, medication use (as appropriate

PROTOCOL
 "P01 Cessation Screening Study"
 PI: [name].; UW-CTRI Grant:

based on study condition), use of alternative nicotine products (e.g., e-cigarettes), withdrawal, self-efficacy, and adverse events. We will recommend dosage/use alterations as per good clinical practice if participants experience adverse events. Participants will be referred to their primary care physician should they require medical consultation. Participants will also receive smoking cessation counseling as appropriate, based on their assigned treatment condition. If the call does not include treatment it will not be conducted by the participant's health counselor (i.e., Calls 5 and 6 for those in the Minimal Counseling condition).

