Effectiveness. We will conduct logistic regression analyses with predictors corresponding to the four factors using effect coding. The logistic regression models will include main and all interactive effects. Main effects will reflect the degree to which participants in the “ON” condition of a factor have significantly higher 1-year point-prevalence abstinence, relative to participants in the “OFF” condition for each factor, averaged across the other factors. These analyses will allow us to identify optimized treatments based upon main effects and interactions as they provide effect sizes (standardized regression coefficients) for the various intervention components and their combinations. Interactions between Medication Type and other factors could potentially yield distinct optimized treatment regimens for C-NRT and varenicline, especially given the frequency of meaningful interactions amongst smoking intervention components. *A priori* we have decided to identify two optimized treatments to allow for patient choice, provide flexibility for patients who may have contraindications, and provide an opportunity for strategic assignment depending on smoker characteristics (algorithm-based personalized medicine). On the other hand, if we obtain a strong main effect for one of the medications (e.g., varenicline), this would be important clinically and would identify one of these agents as the preferred basis for optimized treatment.

The question of primary interest is how treatments affect abstinence amongst diverse smokers amidst the variety of other factors that also influence smokers’ ability to maintain abstinence, not whether such effects occur in a statistically adjusted sample. Therefore, the primary analyses will first be conducted without covariate adjustment, to ensure that covariate adjustment does not cloud interpretation or reduce external validity for various reasons. In additional analyses, we will statistically control for covariates such as healthcare system and clinic, and important smoker characteristics known to affect either treatment response or abstinence likelihood (**biological variables**: e.g., sex and age, as well as other key variables such as living with a smoker, educational attainment) to explore how treatment effects are related to such variables.

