608 (304 in the ON and 304 in the OFF levels of each factor with no missing data because missing=smoking) and $\alpha=.05$, we are powered at .87 to detect a difference between 15% and 25% in 52-week biochemically confirmed abstinence; we also have sufficient power (.81) to detect a difference between 20% and 30% in 52-week biochemically confirmed abstinence. Treatment optimization will be based on the effect size estimates of the main and interactive effects on 12-month abstinence, rather than statistical significance, consistent with our prior research¹⁵.

Protection of Human Subjects

Human Subjects Involvement and Characteristics. All EHR-identified smokers in a clinic will receive an invitation (in their preferred modality: mail, MyChart messages from the EHR, text) to find out more about smoking treatment by calling a healthcare system Care Manager. In addition, Medical Assistants (MAs), using an EHR-guided prompt, will inform all smokers attending in-person or tele-health visits that they will be getting a call from their clinic’s Care Manager, using an opt-out approach. The Care Manager will call the smoker and assess their interest in quitting smoking. Smokers who are interested in quitting in the next 30 days will be offered a variety of cessation treatment options, including the opportunity to participate in this smoking cessation study.

Specific eligibility requirements for this project are: age >17 years; smoking >4 cigarettes/day for the previous 6 months; able to read, write, and speak English; not currently taking bupropion or varenicline; if currently using NRT, agreeing to use only study medication for the duration of the study; medically eligible to use study medications (e.g., no severe renal disease, no allergic reactions to tested agents); and, if the participant is a woman of childbearing potential, using an approved method of birth control during treatment.

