A total of 608 participants will be recruited for this project. No special vulnerable populations will be recruited (pregnant women will be specifically screened out due to medication safety concerns and no persons under the age of 18 will be allowed to participate because the medications we are using have not been approved by the FDA for individuals less than 18 years old). Eligible participants will be randomized following provision of oral informed consent and PCP verification of eligibility (stratified by clinic, gender, and race [white vs. non-white]).

Nicotine patch and varenicline dosing will be consistent with the 2008 PHS Guideline³ and package inserts. All participants in the C-NRT group will receive 2mg mini-lozenges due to the superior palatability of the 2mg lozenges.

- Nicotine patches: ≥10 cigs/day = 8 [or more, depending on treatment condition] weeks of 21 mg, 2 weeks of 14 mg, and 2 weeks of 7 mg nicotine patches; 5-9 cigs/day = 8 [or more, depending on treatment condition] weeks of 14 mg, and 4 weeks of 7 mg nicotine patches;
 - Participants assigned to Preparation NRT will receive 14 mg patches
- Nicotine mini-lozenges: 2mg mini-lozenges;
- Varenicline .5 mg once/day for 3 days, then .5 mg bid for 3 days and then 1 mg bid for the remainder of the regimen.

The study will recommend dosage/use alterations as per good clinical practice if the participant experiences side effects. The Health Counselor will refer participants to their primary care physician should they require medical consultation. Medication is provided to participants in dosage periods defined within each treatment condition (e.g., participants may start their medication 4 weeks prior to the TQD; participants may receive medication for 12 or 24 weeks post-quit).

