Due to delays in implementing the study, and subsequent costs, caused by the global COVID pandemic, we were not able to reach our target sample size of 608. Preliminary data analyses conducted with data collected through December 7, 2023 indicated that there was only one factor that appeared to have a strong main effect for 6-month ($n=432$) and 12-month abstinence ($n=334$). The difference in abstinence rates for the two levels of each of the other 3 factors ranged from 0.0 to 4.9 percentage points. Given the lack of financial resources and the limited signal for additional main effects, we opted to close study recruitment at 538 (88.5% of the sample).

Sample Description

Participants' demographic and baseline smoking characteristics will be summarized using the appropriate descriptive statistics. The 42 people who were assigned varenicline and then discontinued varenicline and were switched to NRT after the FDA recalled Pfizer's varenicline will not be included in the main outcome analyses. We will conduct descriptive analyses to examine the differences between those in the varenicline condition who completed the treatment vs. those who switched to NRT during the FDA recall.

Outcome Analyses

Primary Aim 1: Identifying Main and Interactive Effects on Abstinence. The primary outcome is biochemically confirmed, point-prevalence abstinence (PPA) at 12-months post-TQD (based on $\text{CO} < 6\text{ ppm}$ for those assessed prior to September 2023 or salivary cotinine $\leq 10\text{ng/mL}$ for those assessed from September 2023 onward). We will conduct logistic regression analyses with predictors corresponding to the four factors using effect coding. The logistic regression models will include main and all interactive effects. Main effects will reflect the degree to which participants in the "ON" condition of a factor have significantly higher 1-year point-prevalence abstinence, relative to participants in the "OFF" condition for each factor, averaged across the other factors. These analyses will allow us to identify optimized treatments based upon main effects and interactions as they provide effect sizes (standardized regression coefficients) for the various intervention components and their combinations. We will conduct sensitivity analyses that compute abstinence means for those with CO vs. cotinine bio-verification. Due to the small sample sizes we will not do inferential testing on these comparisons.

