The question of primary interest is how treatments affect abstinence amongst diverse smokers amidst the variety of other factors that also influence smokers' ability to maintain abstinence, not whether such effects occur in a statistically adjusted sample. Therefore, the primary analyses will first be conducted without covariate adjustment, to ensure that covariate adjustment does not cloud interpretation or reduce external validity for various reasons. In secondary analyses, we will statistically control for covariates including: living with a smoker, biological sex, age, clinic, health system, use of other tobacco products at baseline, cigarettes per day at baseline,

and education. In addition, primary analyses will exclude participants who were switched to cNRT from varenicline or stopped using any medication during the FDA varenicline recall.

Self-reported point-prevalence abstinence at Weeks 12 and 26 and biochemically confirmed abstinence at Week 26 will be analyzed as secondary outcomes using methods similar to those used for the primary outcome. These analyses will allow us to examine the stability or robustness of the intervention component effects.

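### The primary factorial model leaves out the randomisation strata and baseline dependence for a reason that does not apply to a standardised risk difference; the cost is a modest loss of precision.

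*SAP*

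**What the plan says.** The protocol (Protection of Human Subjects, Human Subjects Involvement and Characteristics) randomises participants "stratified by clinic, gender, and race [white vs. non-white". At Call 2, the call at which they are randomised, "they will complete the Fagerström Test of Cigarette Dependence" (Protocol, Assessments).

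On the primary model, the SAP (Outcome Analyses, Primary Aim 1) states: "The logistic regression models will include main and all interactive effects". With four two-level factors that is 15 factorial terms plus an intercept. The results are to "provide effect sizes (standardized regression coefficients) for the various intervention components and their combinations". On covariates: "the primary analyses will first be conducted without covariate adjustment, to ensure that covariate adjustment does not cloud interpretation or reduce external validity". The protocol (Analytic Approach, Effectiveness) takes the same position, while describing some of the covariates as "important smoker characteristics known to affect either treatment response or abstinence likelihood".

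An adjusted analysis is planned as secondary: "we will statistically control for covariates including: living with a smoker, biological sex, age, clinic, health system, use of other tobacco products at baseline", followed by cigarettes per day and education. Race and the Fagerström score are not on that list. Neither document plans a standardised risk difference. The standardised regression coefficients in the SAP are a different quantity.

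**The concern.** Two things do not fit together. The trial balanced allocation on clinic, gender and race, but the primary model ignores all three. If the strata predict abstinence, the unadjusted standard error still contains between-stratum variation that the allocation has removed, and the test is slightly conservative. The plan also measures dependence before treatment and does not use it in either the primary or the secondary model.

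The reason given is that adjustment would shift the question to an artificially adjusted sample. That has force against a conditional odds ratio. It has none against standardisation, which predicts each participant's abstinence with a factor ON and then OFF, and averages both over everyone analysed. The population and the marginal effect are those of the unadjusted comparison.

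Precision matters here because recruitment closed at 538 rather than 608 and 42 participants are excluded. Optimisation rests on effect size estimates rather than on significance (Protocol, Sample Size and Power Considerations). In the preliminary data, three factors differed by only 0.0 to 4.9 percentage points (SAP, Implementation Challenges).

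**Working it through.** **1. Reproduce the plan's power.** The protocol assumes "608 (304 in the ON and 304 in the OFF levels of each factor with no missing data because missing=smoking", alpha .05, and claims .87 for 15 vs 25% and .81 for 20 vs 30%. Sidedness is not stated; I take two-sided with pooled variance under the null:

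power = Φ{ [d − 1.96·√(2p̄(1−p̄)/n)] / √(p1(1−p1)/n + p2(1−p2)/n) }

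- n = 304, 15 vs 25%: (0.10 − 0.0636)/0.0322 = 1.131, power .871.
- n = 304, 20 vs 30%: (0.10 − 0.0688)/0.0349 = 0.893, power .814.

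Both agree with the protocol, so the sample-size figures contain no error.

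**2. Move to the analysed sample.** 538 − 42 = 496 if all 42 exclusions are among the 538, and 248 per level if split equally. Power becomes .797 (15 vs 25%) and .731 (20 vs 30%).

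**3. Best-case gain.** If covariates explain a share R² of the outcome variance, the variance of the standardised risk difference is multiplied by about (1 − R²). Effective N is 496/(1 − R²), and the 95% half-width is multiplied by √(1 − R²). R² is my assumption.

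| R² | Effective N | Power, 20 vs 30% | Half-width (points) | Power, 15 vs 25% | Half-width (points) |
|---|---|---|---|---|---|
| 0 | 496 | .731 | 7.57 | .797 | 6.99 |
| .02 | 506 | .740 | 7.49 | .805 | 6.92 |
| .05 | 522 | .753 | 7.38 | .817 | 6.81 |
| .08 | 539 | .766 | 7.26 | .829 | 6.70 |

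539 − 496 = 43 participants at the top of the range, and none at the bottom.

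**4. Does the target effect change?** I simulated N = 496 with the full factorial model, 12 clinics, sex, race and a dependence score (1,200 replicates per setting). The mean unadjusted and standardised adjusted risk differences agreed within 0.0002 in every setting (for example 0.0961 and 0.0960). They estimate the same thing.

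**5. Does the gain survive estimating the covariate terms?** Ratio of adjusted to unadjusted empirical standard error of the risk difference, same simulation:

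| R² (approx.) | 11 clinic terms + sex, race, dependence | Sex, race, dependence only |
|---|---|---|
| 0 | 1.019 | 1.006 |
| .012 | 1.012 | 1.001 |
| .037 | 0.985 | 0.980 |
| .081 | 0.983 | 0.972 |

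At R² of about .08, 0.983 corresponds to 496/0.983² = 513 effective participants and 0.972 to 496/0.972² = 525. Those are gains of 17 and 29, against the ideal 43. With weak covariates the clinic terms cost slightly more than they return. A separate comparison gave ratios from about 1.01 down to 0.96 with 12 clinic terms, and from 1.00 down to 0.96 with health system instead.

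**6. The scale the SAP reports.** In a simulation with one prognostic score (R² about .054), adjustment raised the standard error of the logistic coefficient from 0.1067 to 0.1105. The coefficient grew from 0.274 to 0.292, and power rose from .728 to .755.

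**7. Type I error.** With stratified allocation and no effect, the unadjusted test rejected in .044 and .041 of runs in two settings, against a nominal .05. In the second setting (R² about .11) its model standard error was 0.0358, while the estimate's actual spread was 0.0343.

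**The case against.** The unadjusted primary analysis is a deliberate choice, stated with the same reason in both documents, and an adjusted analysis is already prespecified as secondary with clinic, health system, sex and cigarettes per day. The only variables wholly missing are race and the Fagerström score. On the plan's own effect measure, the logistic coefficient, adjustment widens the standard error. The documents give no prognostic strength, so any gain is assumed, and a realistic model may return little or nothing. Finally, 12-month factor-level results through December 7, 2023 have been examined, so changing the primary analysis now invites the suspicion that the choice was data-driven.

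Most of this stands as a limit on size and as a condition on how the change is made. It does not rescue the stated reason, and the secondary model is not a full substitute: it omits one stratum and the dependence score, and it names no marginal effect.

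A reader might infer more than the documents support:

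- *That the unadjusted results are biased or have inflated false-positive rates.* They do not; if anything the test is slightly conservative.
- *That the intervals for the planned coefficients are wider than they need be.* Those standard errors grow with adjustment; the narrowing belongs to the risk difference.
- *That adjustment restores the planned power.* For 20 vs 30% it stays below .80 throughout the assumed range. For 15 vs 25% the unadjusted figure is already .797.
- *That a definite number of participants is being lost.* The lower end of the range is zero.

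**Conclusion.** The point holds as one of efficiency. The primary model leaves out the three variables used to stratify randomisation and a dependence score already collected, and the external-validity argument does not justify this once the effect is a standardised risk difference. The half-width for 20 vs 30% narrows from 7.57 to at best 7.26 points, and power gains at most about 3.5 points. A model with all clinic terms gains less, possibly nothing. The change is worth making because it needs no new data, but no conclusion of the trial is invalid without it.

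Assumptions: two-sided test; all 42 exclusions among the 538; an equal split per factor, which fits Medication Type least well, since its allocation was C-NRT only for a period and then 2:1; R² between 0 and 8%; and the Fagerström score recorded before the allocation is disclosed within Call 2, the order in which the protocol describes that call.

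**What to change.** Prespecify, for each factor, a standardised risk difference by g-computation with a robust or bootstrap standard error. Take it from the full factorial logistic model plus sex, race, baseline Fagerström score, cigarettes per day and health system. If clinic is preferred to health system, enter it as a random intercept and state how predictions are averaged over clinics. The number of clinics must be reconciled first: the protocol gives 12 under Recruitment & Study Entry and 8 under Recruitment and Informed Consent.

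Keep the protocol's unadjusted model and report it alongside as the sensitivity analysis. Fix the covariate list and date the amendment before the final analysis, with a statement that the preliminary factor-level results did not guide the choice.

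The cost is SAP wording and a few model terms. The downsides are two versions of each effect, slightly more complex reporting, and the need to document that the change was not data-driven.

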We will use multiple criteria decision analysis (MCDA), which focuses on how to weight and combine such criteria to support meaningful decisions and to decide on the optimal treatment packages. We will follow recommendations of the International Society for Pharmacoeconomics and Outcomes Research (ISPOR) Best Practices Task Force^{139,140} with respect to problem definition, criteria selection, use of the value measurement approach, criteria weighting, sensitivity analyses, and so on. We will synthesize cost and effectiveness scores for groupings of intervention components via an additive model with weights for the scores being derived from data generated by assessments of key healthcare system and clinical stakeholders (e.g., physicians, healthcare system administrators; see Implementation Project). The optimized packages will be those that perform best with regard to stakeholder-based preference weightings.

Secondary Aims Analyses. Exploratory analysis of *moderators* of abstinence outcomes will use complementary logistic regression analyses with appropriate model-fitting techniques¹⁴¹ and regression tree analyses that can identify differential treatment responses^{142,143} in 6- and 12-month abstinence. Candidate moderators of treatment effects on abstinence will include tobacco dependence and psychiatric history, contextual factors such as household smoking, and **biological variables** such as sex. In the logistic regression analyses, moderators will be evaluated with regard to their interactions with treatment main effects and interactions. With a similar sample size, we were able to detect moderation in our prior factorial research.

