Primary Aim 2: To identify two optimized smoking cessation treatments: one for varenicline and one for C-NRT. Data on both the 12-month abstinence effect sizes and costs of the different intervention components and combinations of components will be examined and multiple criteria decision analysis will be used to determine how to use each medication so that it is highly effective and but low in cost.

Secondary Aims: To determine: 1) whether person factors (e.g., sex, dependence, psychiatric history) moderate response to different treatment strategies; and 2) which proximal effects of each treatment factor mediate its long-term benefits; and 3) the main and interactive effects of the cessation interventions on cost-effectiveness and the cost-effectiveness of the optimal combinations of components for each medication type.

Implementation Challenges: Pandemic and Varenicline

Study recruitment began in November 2020.

In June 2021 Pfizer found that some lots of varenicline contained elevated levels of a novel nitrosamine that exceeded the level thought to be safe by the FDA for traditional nitrosamines. Therefore, we briefly paused recruitment. When we resumed recruitment, all participants were randomized to the C-NRT level of the Medication Type factor until November 2021 when we received IRB approval to use FDA-approved generic varenicline. When we were able to procure FDA approved varenicline, we changed our randomization ratio on this factor to 2:1 varenicline to C-NRT. When FDA initiated the varenicline recall, there were 42 participants actively taking

varenicline; 26 participants opted to switch to C-NRT and 16 stopped all medication. These 42 participants will not be included in the main outcome analyses.

We experienced significant implementation challenges with collecting in-person breath samples for biochemical verification of abstinence. In September 2023 we transitioned from using exhaled CO to verify abstinence ($\text{CO} < 6\text{ppm}$) to using cotinine assays on mailed saliva samples to verify abstinence ($\text{cotinine} \leq 10\text{ng/mL}$).

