The robustness of the optimized treatments will then be evaluated with regard to other factors such as patient preference and implementation/burden data (e.g., required clinician/staff time). We will conduct sensitivity analyses that vary both the criteria and weightings (derived from stakeholder data) to examine the robustness of the identified optimized care packages.

Secondary Aims Analyses. Analysis of moderators of abstinence outcomes will use regression tree analyses that can identify differential treatment responses in 6- and 12-month abstinence. Candidate moderators of treatment effects on abstinence will include: living with a smoker, biological sex, age, use of other tobacco products at baseline, cigarettes per day at baseline, and education, and psychiatric history. Candidate mediators of cessation treatment effects will be: medication use and side effects, attendance at counseling sessions, withdrawal symptoms (e.g., craving, negative affect, anhedonia), and cessation self-efficacy. Treatment effects will be modeled as main effects and 2-way interactions with the outcomes being 6- and 12-month biochemically confirmed 7-day point-prevalence abstinence. Mediation analyses will use bootstrapped confidence intervals of the mediated effect. Care will be taken to preserve mediator/outcome temporal priority and the occurrence of smoking during the quit attempt will be statistically controlled. Mediation models will include multiple mediators and will use methods developed for use with dynamic mediator assessments (maximum likelihood estimation using hierarchical linear modeling: HLM 5.04).

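### The SAP reduces the protocol's exploratory moderator analysis to regression trees alone, so no estimate or interval is planned for each candidate moderator, and dependence is missing from the candidate list

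*SAP*

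**What the plan says.** Protocol, Analytic Approach, Secondary Aims Analyses. The protocol labels the moderator work exploratory and gives it two methods. The study of moderators "of abstinence outcomes will use complementary logistic regression analyses with appropriate model-fitting techniques", and regression trees are used alongside. The role of the logistic part is explicit: "In the logistic regression analyses, moderators will be evaluated with regard to their interactions with treatment main effects and interactions". On candidates: "Candidate moderators of treatment effects on abstinence will include tobacco dependence and psychiatric history, contextual factors such as household smoking", with sex added as a biological variable. The only support for power is qualitative: "With a similar sample size, we were able to detect moderation in our prior factorial research".

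SAP, Secondary Aims Analyses. One method remains: "Analysis of moderators of abstinence outcomes will use regression tree analyses that can identify differential treatment responses in 6- and 12-month abstinence". The candidates are "living with a smoker, biological sex, age, use of other tobacco products at baseline, cigarettes per day at baseline, and education, and psychiatric history". The exploratory label is not attached to this analysis.

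SAP, Study Overview, Secondary Aims. The first aim is still to determine "whether person factors (e.g., sex, dependence, psychiatric history) moderate response to different treatment strategies".

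**The concern.** The aim asks a question about each of several named person factors. The logistic part of the protocol's plan addresses it factor by factor, because a moderator-by-factor term can be estimated with an interval whether or not it is significant. A tree reports the variables it selects. For a candidate it passes over, the SAP plans no number at all.

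The SAP explains its other departures: the move from CO to cotinine, early closure, and the exclusion of 42 participants. It says nothing about this one. It also states no splitting, pruning or validation rule, and no rule for interpreting a tree without a split.

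Both documents offer strategic assignment by smoker characteristics as a reason for identifying two optimized treatments. If the tree passes over sex or psychiatric history, readers need to know how large a difference in effect remains compatible with the data. The planned output would not tell them.

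**Working it through.** **1. Does any other SAP sentence restore the moderator models?** The nearest is "Treatment effects will be modeled as main effects and 2-way interactions with the outcomes being 6- and 12-month biochemically confirmed 7-day point-prevalence abstinence". It concerns treatment terms, names no moderator, and stands between the list of mediators and the mediation method. The only intervals promised in that section are bootstrapped ones for mediated effects. The logistic moderator models are therefore absent from the SAP.

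**2. Is dependence covered?** The SAP aim names it. The SAP candidate list has cigarettes per day but no dependence measure. The protocol lists tobacco dependence as a candidate and collects the Fagerström Test of Cigarette Dependence at Call 2 (Assessments; Table 1).

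**3. The plan's own power figures.** Neither document gives power or precision for moderators. The main-effect figures (Protocol, Sample Size and Power Considerations: 304 per level, alpha .05) reproduce with a two-sided test and pooled variance under the null:
- 15% vs 25%: (.10 − 1.96·√(2·.20·.80/304)) / √((.1275+.1875)/304) = (.1000 − .0636)/.0322 = 1.13, power .871 (stated .87).
- 20% vs 30%: (.10 − 1.96·√(2·.25·.75/304)) / √((.16+.21)/304) = (.1000 − .0688)/.0349 = .89, power .814 (stated .81).

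**4. Precision of one moderator-by-factor contrast.** The contrast is the factor's effect at one moderator level minus its effect at the other, so four cells contribute: SE = √(Σ p(1−p)/n).

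Assumptions, not stated in the documents: a binary moderator split 50:50, equal cells, and N = 538 − 42 = 496 (the 42 being among the 538, and excluded here as in the main outcome analyses). That gives n = 496/4 = 124 per cell.
- All cells at 20%: SE = √(4·.16/124) = .0718; half-width 1.96·.0718 = 14.1 points.
- Cells 20/20/20/30%: SE = √((3·.16+.21)/124) = .0746; z = .10/.0746 = 1.34; power Φ(1.34 − 1.96) = .27.
- Cells 15/25/20/20%: SE = √((.1275+.1875+.16+.16)/124) = .0716; z = 1.40; power Φ(1.40 − 1.96) = .29.

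**5. Sensitivity, for a 10-point difference in effects.**

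| N | Moderator split | Cell rates (%) | 95% half-width (points) | Power |
|---|---|---|---|---|
| 608 | 50:50 | 15/25/20/20 | 12.7 | .34 |
| 608 | 50:50 | 20/20/20/30 | 13.2 | .32 |
| 538 | 50:50 | 15/25/20/20 | 13.5 | .31 |
| 538 | 50:50 | 20/20/20/30 | 14.0 | .29 |
| 496 | 50:50 | 15/25/20/20 | 14.0 | .29 |
| 496 | 50:50 | 20/20/20/30 | 14.6 | .27 |
| 496 | 80:20, effect in the 20% only | base 15 | 17.1 | .21 |
| 496 | 80:20, effect in the 20% only | base 20 | 18.7 | .18 |

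The conclusion does not depend on which N applies. At N=496 with a 50:50 split, a 20-point difference has power of .75 (20/20/20/40%) to .77 (15/35/20/20%), so only very large moderation is reasonably detectable.

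**6. Link to a tree.** The figures above are for a direct Wald contrast. The SAP gives no split rule, so no split rate can be derived from it. As an illustration only: if a split test were Bonferroni-adjusted over the seven candidates (critical value 2.69), the chance of a split at N=496 with cells 15/25/20/20% would be Φ(1.40 − 2.69) ≈ .10. With the first cell at 15%, the last two at 20% and the second cell raised, it would be about .26 for 15 points and .51 for 20.

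**The case against.** The strongest case against runs as follows, with what stands of each part.

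- **A reader might infer that the trial will report a tree without a split as proof of no moderation.** No sentence in either document says so. What stands is that the SAP has no rule for that outcome and plans no interval to show what it leaves open.
- **A reader might infer that trees yield no estimates.** That is too strong. A tree gives node-level rates or contrasts for the variables it selects. The gap is a pre-specified estimate and interval for every candidate.
- **The tree algorithm is not described.** It may contain its own pruning, validation or intervals. Effects estimated in the data that chose the split tend to be exaggerated, but whether that would go uncorrected here cannot be settled from the documents.
- **The .27 is not a tree's power.** Correct. It also assumes equal cells, whereas the SAP (Implementation Challenges) describes a period of C-NRT only and then 2:1 allocation to varenicline.
- **The protocol does not promise percentage-point contrasts with intervals.** Correct. It promises logistic models with suitable model fitting, which could include dropping terms. The contrast and interval proposed below go beyond its wording.
- **Restoring the models will not rescue power.** Also correct. With 7 × 4 × 2 = 56 tests (moderators, factors, outcomes) and one true effect, the Benjamini-Hochberg threshold is near .05/56 and power falls from .27 to about .02. The gain is in reporting, which is why intervals and not tests should be the main output.
- **The work is exploratory and secondary.** Agreed. The Primary Aim 1 model and the optimization criteria of abstinence and cost do not depend on it.

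**Conclusion.** The concern holds as a gap between the protocol and the SAP in a secondary, exploratory analysis. The SAP drops the logistic moderator-by-treatment models without explanation and leaves trees as the only stated method. It plans no estimate or interval for each candidate, and it omits dependence although the aim names it.

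Under the assumptions in step 4, a moderator-by-factor contrast has a 95% half-width of about 14 points and power of about .27 to .29 for a 10-point difference. At N=608 power would still be only .32 to .34. An observed difference of zero would thus be compatible with true differences of up to about 14 points either way, wider than the 10 points the protocol treats as clinically significant for a main effect. Smaller subgroups or unequal cells make this worse.

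An absent split would be weak evidence against moderation. The documents do not support the further claim that the trial will draw a conclusion of no moderation from it.

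**What to change.** In the SAP, Secondary Aims Analyses:

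1. Restore the protocol's logistic moderator-by-factor models for each of the seven listed candidates, and add the Fagerström dependence score from Call 2. Say whether the protocol's terms for moderator by treatment interaction are kept; they will be less precise still.
2. Report each interaction as the difference in percentage-point effect between moderator levels with a 95% CI, fixing the comparison values in advance for continuous moderators. Treat the intervals as the main output. Apply Benjamini-Hochberg, already used under Additional Analyses, to any p-values.
3. Label both the models and the trees exploratory.
4. Name the tree's splitting and pruning rule, and estimate tree subgroup effects by cross-validation.
5. State that a moderator the tree does not select is not thereby shown to have no effect.
6. State the N for the moderator analyses (538 or 496).

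Cost: SAP wording and a modest set of regressions on data already collected. With eight candidates, four factors and two outcomes there are 8 × 4 × 2 = 64 contrasts, most with wide intervals. Adequate power is not gained, and the primary aims do not change.
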